8.5.4.5 Clinical Laboratory Evaluation

Safety laboratory assessments will be performed as reported in the sec. 2.2 and 2.3. β -HCG Pregnancy test will be performed, if applicable, during the Screening Period and will be repeated at each cycle before study drug administration, per local guidelines, and at the End of Study Visit. Urinalysis will be assessed at Screening, at each day of Visit 1, at Visit 2, at Visit 3 and at the End of Study Visit. The assessment of Anti-HIV Antibodies, Anti-HBcAg antibodies, Anti-HBsAg antibodies, HBV-DNA, HCV-RNA will be performed ONLY during Screening Period. Safety tests will be performed by the local laboratory of participating sites in order to ensure prompt patient management. For the same reason, tests for Anti-HIV Antibodies, Anti-HBcAg antibodies, Anti-HBsAg antibodies, HBV-DNA, HCV-RNA will be performed by local laboratory of participating sites according to local standard procedures. Results of laboratory tests for Anti-HIV Antibodies, Anti-HBcAg antibodies, Anti-HBsAg antibodies, HBV-DNA, HCV-RNA which have been performed within 3 months prior to Screening Period in the context of the standard patient's management (either in the local lab or in a different lab, provided that they comply with local standard procedures) can be reported in the electronic-Case Report Form (eCRF) under Screening Period procedures and in the patient file as a source document. In such a case, there is no need to repeat the above mentioned tests.

Laboratory values have to be transcribed into the eCRF, except for Urinalysis for which only the judgment has to be reported in the eCRF; the Sponsor will be provided with the currently valid version of the respective normal ranges by the site laboratories (any update of reference ranges needs to be notified on an ongoing basis).

The lab print-outs should be identified with the patient number. All print-outs should be dated and signed by the Investigator and stored in the patient's record. Any out of range value shall be clinically assessed by the Investigator.

The volume of blood to be drawn for each set of safety lab tests will amount to a maximum of 15 mL. The following tests will be performed:

Table 4: Blood and urine sample analyte listing

| BIOCHEMISTRY | SERUM VIROLOGY | HAEMATOLOGY | COAGULATION | URINALYSIS |
|--|---|---|--|---|
| Creatinine Uric acid | Anti-HIV Antibodies Anti-HBcAg Antibodies Anti-HBsAg Antibodies HBV-DNA HCV-RNA | Haemoglobin Haematocrit | INR Prothrombin time and/or prothrombin activity Partial thromboplastin time | pH Density |
| Potassium | | RBC count | | Nitrite |
| Phosphorus | | Platelet count MCV WBC count and differential (absolute and %): | | Protein |
| Calcium | | Neutrophil Lymphocyte Eosinophil | | Glucose |
| BUN/Urea Albumin Alkaline phosphatase Glucose Total proteins Total bilirubin and Direct bilirubin ALT and AST LDH GGT Amylase Troponin I or T Sodium Chloride β-HCG (if applicable) | | Basophil Monocytes | | Ketones RBC WBC Epithelial cells Casts Bacteria Yeast Crystals |

8.5.4.6 12-Lead ECG

Twelve-lead ECGs will be performed locally, using standard equipment available at the study sites, during the Screening Period, prior to study drug administration, and 30 minutes after the end of study drug administration at Visit 1 of each cycle and at End of Study Visit.

A standard 12-lead ECG will be performed at rest in the supine position. All ECG print-outs should be identified with patient number, year of birth, and gender, as well as with the date and time of recording. All print-outs should be assessed, dated and signed by the Investigator and stored in the patient's record.

In addition, ECG will be monitored during and up to 30 minutes after each study treatment infusion and any observed abnormalities will be duly recorded.

NOTE:

If ECG monitoring equipment is not available, at Cycle 1 heart rate should be monitored up to 30 minutes after the end of infusion and 12-lead ECG recorded at 30, 60 and 120 minutes during the IV infusion with final 12-lead ECG record at 30 minutes after the end of infusion;

starting from Cycle 2, heart rate should be monitored up to 30 minutes after the end of infusion with final 12-lead ECG record at 30 minutes after the end of infusion.

8.5.5 Study Endpoints

8.5.5.1 Primary Endpoint

Identification of MTD, defined as the highest dose level at which no more than 1 of 6 patients experiences a DLT during the DLT assessment window. In case the prophylactic use of growth factor support is made mandatory by the CRC, MTD with growth factor support will be established. **Identification of DLT**, defined as any of the following adverse drug reactions (ADRs) that will be assessed during Cycle 1:

- any grade ≥ 3 cardiac toxicity, new segmental wall-motion abnormalities, or cardiac troponin I or T elevation of grade 3 or higher;
- any grade ≥ 3 elevations in total bilirubin, hepatic transaminases, or ALP levels; in patients with baseline grade 2 hepatic transaminase or ALP levels, an elevation to $\geq 10 \times$ ULN is considered a DLT;
- any grade 3 non-haematologic toxicity lasting > 7 days, (excluding diarrhea/nausea for which no adequate and optimal therapy has been implemented and alopecia);
- any grade 3 vomiting lasting > 3 days despite adequate and optimal therapy;
- any grade ≥ 4 non-haematologic toxicity;
- any grade 4 thrombocytopenia or anemia;
- any grade 4 neutropenia lasting > 7 days or febrile neutropenia;
- any treatment delay of > 2 weeks because of delayed recovery from toxicity related to MEN1309 (except for alopecia).

In case neutropenia will be established as the only DLT, the study will continue with the assessment of DLT of MEN1309 given together with routine prophylaxis with growth factors.

Upon the prophylactic use of growth factor support for neutropenia is made mandatory by the CRC, the DLT criterion related to grade 4 neutropenia will change as follows:

- any grade 4 neutropenia lasting > 5 days or febrile neutropenia despite the use of growth factor support.

Although dose escalation is primarily based on the incidence of DLTs during Cycle 1, toxicities that

meet criteria for DLTs and are observed during Cycle 2 or subsequent cycles are also taken into account for the assessment of toxicity and definition of MTD.

8.5.5.2 Secondary Endpoints

- **Preliminary antitumor activity**

Step 1 (solid tumors): is assessed in terms of Response Rate (RR), Disease Control Rate (DCR) and duration of response (DOR). RECIST 1.1 assessment will be performed using CT scan or MRI of the chest and abdomen (including adrenal glands). Any other areas of disease involvement should be additionally investigated based on signs and symptoms of individual patients. For the baseline assessment, CT scan or MRI should be performed no more than 6 weeks (4+2 weeks) before the treatment start. Follow-up assessment will be performed every 2 cycles during study treatment (within a window of -7/+3 days of the scheduled date and in any case before the study drug administration of the subsequent Cycle) until objective disease progression as defined by RECIST 1.1 or at the End of Study Visit. Any other site at which new disease is suspected should be appropriately imaged. If an unscheduled assessment is performed and the disease has not progressed, every attempt should be made to perform the subsequent assessments at their scheduled visits.

Step 2 (NHL): is assessed in terms of CR, PR, and DOR. Cheson Criteria assessment (The Lugano Classification, 2014) will be performed using CT/PET-CT scan or MRI of chest and abdomen (including adrenal glands). Any other areas of disease involvement should also be investigated based on signs and symptoms of individual patients. For the baseline assessment, CT/ PET-CT scan or MRI should be performed no more than 6 weeks (4+2 weeks) before the treatment start. Follow-up assessments will be performed every 2 cycles during study treatment (within a window of -7/+3 days of the scheduled date and in any case before the study drug administration of the subsequent Cycle) for a total of 8 cycles or until objective disease progression as defined by Cheson Criteria (The Lugano Classification, 2014) or at the End of Study Visit. Any other site at which new disease is suspected should be appropriately imaged. If an unscheduled assessment is performed and the disease has not progressed, every attempt should be made to perform the subsequent assessments at their scheduled visits.

- **Preliminary clinical efficacy**

Overall Survival is defined as the number of days between the first study drug administration and death from any cause. Patients without the event are censored to the last date of follow-up.

Progression free survival is defined as the number of days between the first study administration to the date of first documented disease progression, relapse or death from any

cause. Responding patients and patients who are lost to follow-up are censored at their last tumor assessment date.

8.5.5.3 Exploratory endpoints

- To determine the correlation between free CD205 at baseline with clinical activity of MEN1309.
- To determine the correlation between CD205 expression and clinical activity of MEN1309. Protein expression will be assessed through IHC centrally evaluated on archived and, when available, new bioptic tissue samples.
- To determine the DNA sequence of CD205 (at baseline).
- To determine CD205 expression by flow cytometry on peripheral blood cells (at baseline).

8.5.5.4 Immunogenicity Endpoints

- Incidence of anti-MEN1309 auto-antibodies.

8.5.5.5 Pharmacokinetic Endpoints

The following PK variables will be assessed for MEN1309, tAb, DM4 and its metabolite S-methyl-DM4, when applicable: C_{max} , t_{max} , C_{last} , t_{last} , C_{trough} , k_e , $t_{1/2}$, $AUC_{(0-t)}$, $AUC_{(0-\infty)}$, % AUC_{ex} , CL, V_{ss} , V_d , $AUMC_{(0-\infty)}$, MRT, and Ro.

PK parameters will be calculated after the first and second infusion of each dose cohort. C_{max} and C_{trough} will also be obtained after each administration of MEN1309.

8.5.5.6 Safety Endpoints

- Incidence, intensity, CTCAE version 4.03 grading, seriousness and treatment-causality of TEAEs.
- Frequency of clinically significant abnormalities in physical examination, safety laboratory tests, urinalysis, vital signs, and 12-lead ECG record.

8.6 ADVERSE EVENT DEFINITIONS, MONITORING/RECORDING AND MANAGEMENT

8.6.1 Definitions

8.6.1.1 Adverse Event (AE)

Any untoward medical occurrence in a patient or clinical study patient administered a medicinal product and which does not necessarily have a causal relationship with this treatment.

An AE can therefore be any unfavorable and unintended sign (including an abnormal laboratory finding), symptom, or disease temporally associated with the use of a medicinal product, whether or not considered related to the medicinal product.

8.6.1.2 Drug Relationship

The relationship between an AE and study drugs will be judged according to the following categories:

1. **Certain:** The event or laboratory test abnormality (AE) occurs in a plausible time relationship to the drug intake and it cannot be explained by a concurrent disease or other drugs. The response to withdrawal of the drug (dechallenge) should be clinically plausible. The event must be definitive pharmacologically or phenomenologically (i.e., an objective and specific medical disorder or a recognized pharmacological phenomenon), using a satisfactory rechallenge procedure if necessary.
2. **Probable:** The event or laboratory test abnormality (AE) occurs in a reasonable time relation to the administration of the drug, it is unlikely to be attributed to a concurrent disease or other drugs and it follows a clinically reasonable response on withdrawal (dechallenge). Rechallenge (AE reappearance after drug reintroduction) is not required.
3. **Possible:** The event or laboratory test abnormality (AE) occurs with a reasonable time relation to the administration of the drug, but it could also be explained by a concurrent disease or other drugs. Information on drug withdrawal (dechallenge) may be lacking or unclear.
4. **Unassessable:** The relationship cannot be judged, because of the information is insufficient or contradictory and data cannot be supplemented or verified.
5. **Unlikely:** The event or laboratory test abnormality (AE), with a time to drug intake that makes a relationship improbable (but not impossible). Disease or other drugs provide plausible explanations.
6. **Not Related:** The event or laboratory test abnormality (AE), with a time to drug intake with an unreasonable relationship and or non-plausibility and/or the existence of a clear alternative explanation.

8.6.1.3 Adverse Drug Reactions (ADRs)

ADRs are all untoward and unintended responses to an investigational medicinal product related to any dose administered. The definition covers also medication errors and uses outside what is foreseen in the protocol, including misuse and abuse of the product.

The definition implies a reasonable possibility of a causal relationship between the event and the IMP. This means that there are facts (evidence) or arguments to suggest a causal relationship.

ADRs are considered all AEs for which the relationship is considered as:

1. Certain

2. Probable
3. Possible
4. Unassessable

AEs are not considered as ADRs when the relationship is judged as:

5. Unlikely
6. Not related

8.6.1.4 Seriousness

SAE means any untoward medical occurrence that at any dose:

- results in death;
- is life-threatening;
- requires inpatient hospitalization or prolongation of existing hospitalization;
- results in persistent or significant disability/incapacity;
- results in congenital anomaly/birth defect;
- is another medically important condition that may jeopardize the patient or may require intervention to prevent 1 of the outcomes listed above. Any suspected transmission of an infectious agent via a medicinal product is considered serious and should be assessed under the category of medically important events in the absence of other seriousness criteria.

NOTES:

- These characteristics/consequences have to be considered at the time the event occurs. For example, regarding a life-threatening event, this refers to an event in which the patient was at risk of death at the time of the event; it does not refer to an event which hypothetically might have caused death if it were more severe.
Any other AE/ADR which is not included in the above definitions will be considered as non-serious (NSAE/NSADR).
- Hospitalization for chemotherapy administration shall not qualify as adverse event.
- After the End of Study Visit (or later than 28 days after the last study drug administration), fatal outcome related to disease progression will not be reported as AE.

8.6.1.5 Adverse Event (AE)/Adverse Drug Reaction (ADR) Intensity (Severity)

The intensity level of a Serious or a Non-serious AE or ADR is attributed according to the following definitions:

- **Mild:** does not interfere with routine activities; in case of laboratory tests, when there is a mild abnormality.

- **Moderate:** interferes with the routine activities; in case of laboratory tests, when there is a moderate abnormality.
- **Severe:** makes it impossible to perform routine activities; in case of laboratory tests, when there is a significant abnormality.

In addition, the Investigator will adopt the NCI-CTCAE v4.03 (13).

8.6.1.6 Adverse Drug Reaction (ADR) Expectedness

An ADR is considered unexpected when the nature, intensity, or outcome of which is not consistent with the product information provided in the Reference Safety Document (MEN1309 Investigator's Brochure, last version).

8.6.1.7 Serious Unexpected Adverse Drug Reaction (SUSAR)

Any serious adverse event judged by the Investigator or the Sponsor as drug-related (see §8.6.1.2), and considered as unexpected qualifies as a serious unexpected ADR (SUSAR).

SUSARs are subject to expedited reporting, as specified in §8.6.3.2, as having a "Reasonable Possibility" of relationship with the IMP.

8.6.2 Monitoring and Recording of Adverse Events

At each visit the Investigator will assess any occurred subjective or objective AE, starting from the informed consent signature to the End of Study Visit or 28 days after last treatment study drug administration whichever occur last.

AEs communicated by the patient or by the patient's relatives or delegates through phone calls, letters or emails will also be recorded. In these cases the Investigator will try to obtain medical confirmation and assessment of the occurred AE.

When an AE has occurred, the **Investigator shall record on the respective eCRF-AE recording pages any case, both serious and non-serious, whether or not thought to be drug-related**, observed in or reported by the patient (or relatives/delegates), specifying the judgement on the causal relationship with the study treatment.

Any available information and diagnostic measure (laboratory and instrumental tests, procedures, etc.) shall be recorded in the eCRF.

In addition, if after the end of the study the Investigator becomes aware of any AEs or follow-up in AEs already recorded, this information can be recorded in the eCRF until it is available.

8.6.3 Management of Serious Adverse Events (SAEs)

8.6.3.1 Reporting Duties of the Investigator

[figure not shown]
The Investigator must record and save all the available information concerning any SAE (whether or not deemed related to the investigational drug) in the corresponding section of the eCRF, eCRF-AE pages, **no later than 24 hours** after the first knowledge of the occurrence of the event.

When the site personnel enter a new SAE/Case in the eCRF, an automatic alert notification will be generated and sent to the Sponsor's Drug Safety Manager (DSM).

The Investigator will be provided with the paper CRF-AE pages to be used only in case of breakdown of the eCRF System. In such case, the Investigator will be responsible for sending the paper CRF-AE pages form **no later than 24 hours** after the first knowledge and inserting the data in eCRF as soon as the system works again.

Whenever the paper CRF-AE pages are used, they must be submitted by e-mail to the Sponsor's DSM:

Sponsor's DSM contact details:

For the initial SAE the Investigator should enter at least the following data:

- AE medical term.
- Seriousness criteria.
- Causality assessment.
- Study Code and Patient Identification (patient number) [when the paper CRF-AE pages are used].
- Reporter's name and telephone number for clarification [when the paper CRF-AE pages are used].

If not already reported, the full description of the event and outcome must follow within 1 working day.

The Sponsor's confirmation of reception of the AE report must be kept in the patient's records.

Any questions arising during the processing and medical review of the SAE will be managed by means of electronic queries (i.e., queries in the eCRF). In case of a breakdown of the eCRF System, queries will be sent by e-mail.

Any information provided by the Investigator as a query reply or as a follow-up AE report will be

processed in the same way as the initial AE report within the required timeframe.

When relevant, the eCRF pages concerning medical history, concomitant medication, and laboratory tests will also be retrieved by the Sponsor's DSM.

Any further significant information and supporting documentation that become available (such as copies of laboratory reports, tests, procedures, autopsy evidence of the cause of death, etc.) shall be provided by email to the Sponsor's DSM no later than 24 hours after they become known by the Investigator.

The Investigator must also comply with the local applicable obligation(s) on the reporting of ADRs to the local concerned Regulatory Authority/Ethics Committee if required according to the specific country requirements.

8.6.3.2 Reporting Duties of the Sponsor

The Sponsor shall ensure that all relevant information about any suspected serious and unexpected adverse drug reaction (SUSAR), will be expeditiously reported to the Competent Authorities (including EudraVigilance Clinical Trial Module for clinical trials for which a EudraCT number has been assigned) and Ethics Committees (following general and local rules and procedures), with these deadlines after the first knowledge, intended as the day when the Sponsor's DSM or CRO receives the notification of the SUSAR:

- Fatal and life threatening unexpected cases, no later than 7 days;;
- Other unexpected serious cases, no later than 15 days.

The Sponsor shall ensure that all relevant new information will be also expeditiously reported as follow-up information within 15 days for all cases.

The following safety issues will be subjected to expedited management for the identification of possible necessary actions:

- SAEs associated with the study procedures;
- Potential clinically significant findings emerging from non-clinical studies;
- An anticipated end or suspension for safety reasons of another study with the same study drug.

When appropriate and applicable the Sponsor will arrange the adequate information also to the Investigators.

8.6.4 Management of Non-Serious Adverse Events (NSAEs) and/or Laboratory Abnormalities

The Investigator must record all the available information concerning any NSAE (whether or not deemed related to the investigational drug) in the corresponding section of the eCRF, eCRF-AE pages, **within 5 calendar days** after the first knowledge of the occurrence of the event.

When the site personnel enters a new AE/Case in the eCRF, an automatic alert notification will be generated and sent to the Sponsor's DSM.

When relevant, CRF pages concerning medical history, concomitant medication, and laboratory test will also be retrieved by the Sponsor's DSM.

Any further significant information and supporting documentation that become available (such as copies of laboratory tests, procedures, etc.) shall also be provided by the Investigator through additional written reports to the Sponsor's DSM.

In addition, during the clinical study, abnormalities in laboratory analyses (newly occurring after ICF signature or worsening of previously known abnormalities), which are considered clinically relevant by the Principal Investigator (such as values significantly above or under normal range or which require an intervention or diagnostic tests, or may result in the IMP discontinuation), should be reported as AEs. However, all abnormalities in laboratory values should be collected and reviewed by Sponsor on a bi-monthly basis.

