At the time Protocol Version 3.0 is running, the dose cohort of 1.60 mg/kg has been successfully completed in Step 1, therefore the dose escalation in Step 2 will start at 0.80 mg/kg (or at lower level as per decision of the CRC).

In both Step 1 and Step 2, if 2 or more patients experience a DLT at any dose level, further enrolment at that dose level and further dose escalation will cease, and the previous dose level will be defined as the MTD. However, if ≥ 2 DLTs occur during the dose escalation, an intermediate dose level can be evaluated prior to defining the previous dose level as MTD. Upon MTD definition, the MTD cohort in both Step 1 and Step 2 will be expanded up to a total of 10 patients to further explore the safety profile of MEN1309.

In both Step 1 or Step 2, each dose level escalation (or de-escalation) at the pre-defined dose level of MEN1309 or at any intermediate dose levels will be subject to the assessment of the CRC which consists of the Principal Investigators and the Sponsor's qualified Medical Representatives (and invited experts when needed). In addition the CRC has the duty to drive any adjustment in premedication and concomitant medication. The CRC decisions will be immediately implemented and notify to the CA/EC, when appropriate. At the time the Step 2 is open, the CRC will include investigators who are experts in the field of NHL.

The overall study duration will depend on the number of escalating dose levels/cohorts and the number of patients by cohort, as described in the above sections.

All patients will undergo a 12-week Pre-Screening Period followed by a 4-week Screening Period. The Pre-screening Period in patients who are CD205 positive can be extended up to the time they undergo the Screening Visit.

Each treatment cycle will last approximately 3 weeks.

Individual study duration will depend on the duration of study treatment which continues up to disease progression for solid tumors and up to 8 cycles for NHL (further cycles beyond the 8th cycle may be allowed for patients who still benefit from the treatment based upon the Investigator's medical judgement and medical monitor approval).

The End of Study Visit will be performed within 6 weeks after the last administered dose or at the time of study withdrawal/treatment discontinuation of study drug.

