8.4.2 Step 1 dose escalation and cohort expansion in solid tumors

In Step 1, MEN1309 will be administered to escalating dose cohorts encompassing 1 single patient per cohort, starting from the 0.05mg/kg dose along the initial ATD phase, MEN1309 dose will double dose steps per dose level until grade ≥ 2 drug-related toxicity is observed in the 21-day period following the first dose of MEN1309. At that study point, the dose escalation has to follow a modified Fibonacci sequence.

NOTE: During the ATD, the patient who experiences ADR ≥ 2 but not meeting DLT criteria will continue with the assigned dose level.

Along dose escalation following a modified Fibonacci sequence, the dose increments become smaller as the dose increases (i.e., dose-increase by 67%, 50%, 40% and 35% of the preceding doses) and a minimum of 3 patients per cohort are to be enrolled with a minimum 7-day stagger between patients is required to allow the evaluation/interpretation of any adverse events/reactions prior to expose other patients to the same dose of MEN1309.

Any cohort in which 1 patient experiences a DLT during the DLT assessment window (the 21-day period following the first administration of MEN1309) **will be expanded to a total of 6 patients**, with a minimum 24 hours stagger between the 3 additional patients.

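### A non-serious DLT has no reporting deadline of its own, so under the 5-day rule for non-serious events patients staggered by 24 hours could be dosed after the second DLT that should close the dose level

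*Protocol*

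**What the plan says.** **Reporting.** For a serious adverse event, protocol section 8.6.3.1 requires the site to record it "no later than 24 hours after the first knowledge of the occurrence of the event". For a non-serious one, section 8.6.4 requires entry on the "eCRF-AE pages, within 5 calendar days after the first knowledge of the occurrence of the event". On entry, "an automatic alert notification will be generated and sent to the" Sponsor's Drug Safety Manager. Laboratory abnormalities that the Principal Investigator considers clinically relevant are to be reported as adverse events.

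**DLTs.** Section 8.5.5.1 (repeated in SAP section 5.1.1.1) lists the criteria. DLTs and serious events appear as separate items in sections 8.2.3 and 8.3.3, and the Sponsor's expedited-management list in section 8.6.3.2 does not mention DLTs.

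**Stopping rule.** Section 8.1, and again the note in 8.4.3, says that "if 2 or more patients experience a DLT at any dose level, further enrolment at that dose level and further dose escalation will cease". About 8 sites take part.

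**Stagger.** A cohort with one DLT is expanded to six, "with a minimum 24 hours stagger between the 3 additional patients" (section 8.4.2; also the synopsis, section 8.1 and SAP section 3.1.1.1). Section 6.3, item 5, instead states a minimum of 7 days for expanding the number of patients within a dose level.

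**Committee.** Under section 8.7 the Cohort Review Committee (CRC) meets before each escalation and at other times as needed. No meeting triggered by a DLT within a cohort is described.

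**The concern.** The stop at two DLTs is the main protection for patients at a given dose level, and in a multi-site trial it can act only on DLTs that the other sites know about. Several criteria can be met without meeting a seriousness criterion in section 8.6.1.4: grade 3 elevation of transaminases, bilirubin or alkaline phosphatase, grade 4 thrombocytopenia, or afebrile grade 4 neutropenia lasting more than 7 days. A site that takes the full 5 days to enter such an event complies with the protocol, and the automatic alert does not fire until it does. Meanwhile another site, also in compliance, may dose a further patient at a level where enrolment should already have ceased.

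Expansion after a first DLT has already happened once: section 6.2.3 reports that the 1.60 mg/kg cohort was expanded to six patients for this reason.

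**Working it through.** The plan gives no figure for this, so there is none to reproduce. The check is a timeline.

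**Inputs**
- Reporting lag L: 5 × 24 = 120 h for a non-serious event (section 8.6.4); 24 h for a serious one (section 8.6.3.1).
- Stagger s: 24 h (section 8.4.2), or 7 × 24 = 168 h (section 6.3, item 5).
- Additional patients: three (patients 4, 5 and 6), dosed at 0, s and 2s hours.
- T: the time, counted from patient 4's dose, at which the second DLT is first known at its own site.

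**Assumptions.** Dosing runs at the minimum stagger. The site uses its whole allowance. The other sites learn of the event at T + L, with no informal contact before then and no relay delay after it.

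**Rule.** A patient is dosed after the second DLT but before it is reported if the dosing time d satisfies T < d ≤ T + L. A window of length L holds at most L/s doses, rounded up, and never more than the number of patients still to be dosed.

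**Results**

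| Stagger | Lag | When the second DLT is known | Patients dosed in the window |
|---|---|---|---|
| 24 h | 120 h | T = 0 (patient 4 being dosed) | d = 24 and 48: 2 |
| 24 h | 120 h | before T = 0, up to 72 h earlier | d = 0, 24 and 48: 3 |
| 24 h | 24 h | any T | 24/24 = 1, so at most 1 |
| 168 h | 120 h | any T | 120/168 = 0.71, so at most 1 |

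The 72-hour limit in the second row comes from 48 ≤ T + 120, so T ≥ −72. In the first row, entry is not due until 120 − 48 = 72 h after patient 6 is dosed. Section 10.1.1 has a general eCRF allowance of 5 working days, about 7 calendar days; a 168 h lag leaves the maxima at 2 and 3 under the 24-hour stagger and 1 under the 7-day stagger.

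**Whose DLT it can be.** A second DLT known at or before T = 0 must be in one of patients 1 to 3. No section expressly requires all three to finish their 21-day window before the expansion opens, so this is possible. If the second DLT is in patient 4, the lag matters only when the event is known within 48 h of that patient's dose: patients 5 and 6 are both exposed if it is known in the first 24 h, and patient 6 alone if between 24 and 48 h.

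**Illustration of consequence.** The documents give no DLT rate, so p is assumed. The chance of at least one further DLT among k extra patients is 1 − (1 − p)^k.

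| Assumed p | k = 1 | k = 2 | k = 3 |
|---|---|---|---|
| 17% | 17% | 31% | 43% |
| 33% | 33% | 55% | 70% |
| 50% | 50% | 75% | 88% |

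**The case against.** **The stagger is contested.** The counts of 2 and 3 use only the 24-hour text. Under the 7-day text in section 6.3 the maximum is 1, even with the 5-day lag. This stands, and it makes 2 to 3 a worst case. The missing DLT deadline remains under either text.

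**Reporting speed is often not the cause.** At the minimum 24-hour stagger all three patients are dosed within 48 h. Grade 4 neutropenia lasting more than 7 days cannot be established in patient 4 by then, and section 6.3 puts the observed nadir at Day 15. Such DLTs in patients 4 to 6 would come too late even with instant reporting. This also stands. The lag matters for an early DLT in patient 4, for a second DLT among patients 1 to 3 while the expansion is open, or when accrual is slower than the minimum. In the last case fewer patients fall within the lag: with gaps of 5 days or more, at most 1.

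**Other safeguards exist.** Five days is a ceiling, section 5.9 provides for urgent safety measures, investigators sit on the CRC, and the medically important criterion in section 8.6.1.4 can make some DLTs serious. These help, but they rest on judgement, and none sets a time for reporting a DLT.

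**The CRC Charter and Data Review Plan were not available.** A faster notice there cannot be excluded. However, section 8.7 describes the Charter as covering roles, meeting schedule and format of information, and section 9.5 describes the Data Review Plan as covering the data supplied before CRC meetings. Neither is described as setting a site deadline.

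**A stronger reading that fails.** Because "all abnormalities in laboratory values should be collected and reviewed by Sponsor on a bi-monthly basis", a reader might infer that laboratory DLTs wait for that review. The documents do not support this. The same section makes clinically relevant abnormalities adverse events, and its examples include values far outside the normal range or that may lead to stopping the study drug; a Cycle 1 DLT is itself a withdrawal criterion in section 8.2.3. Section 8.5.4.5 adds: "Any out of range value shall be clinically assessed by the Investigator". A DLT-level value would therefore normally fall under the 5-day or 24-hour rule, and the bi-monthly review is additional.

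**Conclusion.** The concern holds as a gap in the reporting rules. The protocol sets no DLT-specific deadline and no route by which a DLT at one site reaches the others, and a non-serious DLT falls under the 5-calendar-day rule. With the 24-hour stagger, dosing at the minimum interval and full use of the allowance, up to 2 patients, or 3 if the second DLT was known up to 72 hours before patient 4, can be dosed at a level that already meets the stopping rule. A 24-hour deadline brings the maximum to 1. These are upper bounds, not expected numbers, and the conflict between the 24-hour and 7-day staggers must be resolved before either bound can be relied on.

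Two further inferences go too far. A DLT count that is incomplete mid-cohort does not by itself bias the maximum tolerated dose, because the CRC assesses all data at the end of each dose level and DLT evaluability requires 21 days of follow-up. Nor is there much need to extend the point to the accelerated titration phase, since section 6.2.3 says Step 1 has already moved to the 3+3 design.

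**What to change.** In sections 8.6.3.1 and 8.6.4:

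1. Require any event that meets, or may meet, a DLT criterion to be entered on the eCRF adverse event page within 24 hours of first knowledge, whether or not it is serious. The existing automatic alert then does the notifying.
2. Require any Cycle 1 laboratory value that meets a DLT threshold to be recorded as an adverse event, without a separate judgement of clinical relevance. Whether it is drug-related, and so a DLT, is still assessed in the usual way.
3. Have the Sponsor confirm the current DLT count at the dose level before each further patient is assigned to it, at the existing Day 1 dose cohort assignment step in section 8.5.1.

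Separately, reconcile the stagger in section 6.3, item 5, with that in the synopsis and sections 8.1 and 8.4.2. If the CRC Charter already sets a site deadline for DLTs, a cross-reference in section 8.6.4 would cover item 1.

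The cost is protocol wording and eCRF guidance, with a few adverse event pages entered sooner. No visits, tests or patients are added.
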